12.5 STUDY OUTCOMES

Efficacy outcomes for this study will include:

- Total meibomian gland secretion score (MGSS) computed as the sum of the grades for all 15 glands evaluated on the lower eyelid with a range from 0 to 45.

- Lid margin erythema

The primary safety endpoint of this study is incidence of treatment-related adverse events (AE). Descriptive statistics of adverse events will be provided, as will narratives of any serious, unexpected, drug-related AEs. Any clinically meaningful changes in visual acuity or slit lamp biomicroscopy findings will be tabulated.

12.6. STATISTICAL HYPOTHESES

For the comparisons between dosing regimens, the null hypothesis is the efficacy outcomes for the dosing regimens is equal. The alternative hypothesis is the efficacy outcomes are not equal, ie a two-sided test. The hypothesis can be expressed as follows:

$$H_0: E_1 = E_2$$

$$H_A: E_1 \neq E_2$$

where E_1 and E_2 are the efficacy outcomes for each dosing regimen.

For the analyses of the change from baseline in efficacy outcomes for both treatments combined, the null hypothesis is there is no difference between the baseline and follow-up values. The alternative hypothesis is the follow-up outcome has improved from baseline. The hypothesis can be expressed as follows:

$$H_0: D \leq 0$$

$$H_A: D > 0$$

[figure not shown]
where D is the improvement from baseline (note, for some variables, an improvement may be a decrease from baseline).

12.7. STATISTICAL ANALYSES

Efficacy Analyses

Efficacy analyses comparing the outcome between dosing regimens will be performed on the change from baseline, except for the post treatment survey, using either the Student's *t*-test or Wilcoxon rank-sum test as appropriate.

Efficacy analyses examining the change from baseline for both dosing regimens combined will use either a paired *t*-test or a Wilcoxon signed-rank test as appropriate. A one-sided test for an improvement from baseline will be evaluated using an α of 0.025.

Safety Analyses

Clinically meaningful changes from baseline (Day 1) in visual acuity and slit lamp biomicroscopy will be summarized for each follow-up visit. A clinically meaningful change for visual acuity will be a change of more than 2 lines on the ETDRS chart (change greater than 0.2 logMAR). A clinically meaningful change in slit lamp biomicroscopy will be a change of 2 or more grades.

Adverse event data will be summarized by the MedDRA preferred term and listed.

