**Randomized, Double-Masked, Pilot Study Comparing the Safety and Efficacy
of Two Dosing Regimens of TP-03 for the Treatment of Meibomian Gland
Dysfunction in Patients with *Demodex* Lid Infestation (Ersa)**

Protocol Number: TRS-008

[REDACTED]

[REDACTED]

[REDACTED]

[REDACTED]

IND Sponsor: Tarsus Pharmaceuticals, Inc.

NCT05454956

PROTOCOL SUMMARY

TITLE	Randomized, Double-Masked, Pilot Study Comparing the Safety and Efficacy of Two Dosing Regimens of TP-03 for the Treatment of Meibomian Gland Dysfunction in Patients with Demodex Lid Infestation (Ersa)
TEST ARTICLE	TP-03, lotilaner ophthalmic solution, 0.25%
OTHER TEST ARTICLE	Vehicle of TP-03 to maintain masking of BID dosing
OBJECTIVE	
To evaluate the safety and efficacy of TP-03, 0.25%, BID versus TID dosing for the treatment of meibomian gland dysfunction in patients with Demodex lid infestation.
 
Efficacy will be evaluated by the assessment of lower lid meibomian gland secretion, erythema of the lid margins, [REDACTED], [REDACTED].
 
Safety will be determined by assessing adverse effects related to treatment [REDACTED]
 
[REDACTED]

CLINICAL HYPOTHESIS	Treatment with TP-03, 0.25%, TID will result in a greater improvement from baseline than BID treatment for 85 days in the signs [REDACTED] of MGD with no significant increase in ocular irritation.
STUDY DESIGN	Prospective, randomized, two-arm, double-masked, parallel treatment study
NUMBER OF PARTICIPANTS	Up to 40
PARTICIPANT POPULATION	Participants with evidence of meibomian gland dysfunction in the presence of Demodex infestation
DESCRIPTION OF SITES	Up to six sites in the United States
STUDY DURATION	Approximately 9 months
RANDOMIZATION	1:1
STUDY VISITS	Study visits will take place at Day 1, Day 15, Day 29, Day 43, Day 57, Day 85 and Day 115
SAFETY MEASURES	
 • Adverse events • [REDACTED] • Slit lamp biomicroscopy findings
EFFICACY MEASURES	
 • Lower lid meibomian gland secretion assessment 
 ○ Total meibomian gland score

Clinical Research Protocol

Protocol TRS-008

[figure not shown]
01-Feb-2023

	
• Lid margin erythema

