STATISTICAL CONSIDERATIONS	This is a pilot study to compare the safety and efficacy of two different dosing regimens, BID and TID, of TP-03 for the treatment of MGD. There are no prior data available to perform a sample size estimate. The sample size of 40 participants was selected based on clinical and practical considerations.
STATISTICAL ANALYSIS PLAN	
Safety measures will be summarized for each treatment regimen and both treatment regimens combined using descriptive statistics.
 
Efficacy measures will be compared between dosing regimens as the change from baseline using either the t-test or Wilcoxon rank-sum test as appropriate. Comparisons will be two-sided using an α of 0.05. No adjustment will be made for multiple comparisons.

TABLE OF CONTENTS

1.	ABBREVIATION TABLE.....	7
2.	INTRODUCTION AND RATIONALE.....	8
2.1.	MEIBOMIAN GLANDS	8
2.2.	MEIBOMIAN GLAND DYSFUNCTION	8
2.6.	POTENTIAL RISKS AND BENEFITS	13
3.	TREATMENTS.....	14
3.1.	TP-03 AND VEHICLE	14
4.	STUDY OBJECTIVE.....	15
5.	STUDY DESIGN.....	15
6.	STUDY POPULATION	15
7.	STUDY OUTCOME MEASUREMENTS.....	18
7.1.	EFFICACY PARAMETERS.....	18
7.2.	SAFETY PARAMETERS	18
8.	CLINICAL EVALUATIONS	18
8.1.	DAY 1	18
8.2.	DAYS 15 (± 4 DAYS) AND 29 (± 5 DAYS)	19
8.3.	DAY 43 (-7/+6 DAYS) AND DAY 57 (-7/+10 DAYS).....	20
8.4.	DAY 85 (-13/+7 DAYS).....	20
8.5.	DAY 115 (+60 DAYS)	21
9.	STUDY DRUG	21
10.	STUDY PROCEDURES AND ASSESSMENTS	22
10.1.	INFORMED CONSENT	22
10.2.	PARTICIPANT ID ASSIGNMENT.....	22
10.3.	STUDY TREATMENT COMPLIANCE	23
10.4.	VISIT SCHEDULE AND EXAMS	23
10.5.	STUDY EXIT	23
11.	EARLY TERMINATION AND PARTICIPANT DISCONTINUATION.....	23

12. STATISTICAL CONSIDERATIONS AND ANALYSIS	25
12.1. SAMPLE SIZE	25
12.2. RANDOMIZATION.....	25
12.3. GENERAL CONSIDERATIONS	25
12.4. MISSING DATA	25
12.5. STUDY OUTCOMES	25
12.6. STATISTICAL HYPOTHESES.....	26
12.7. STATISTICAL ANALYSES	26
12.8. INTERIM ANALYSIS	27
12.9. FINAL REPORT	27
13. ETHICAL AND REGULATORY CONSIDERATIONS	27
14. INVESTIGATOR RESPONSIBILITIES.....	28
15. CONCOMITANT MEDICATIONS AND THERAPIES	29
15.1. PROHIBITED CONCOMITANT MEDICATIONS/PROCEDURES	29
16. ADVERSE EVENTS AND SERIOUS ADVERSE EVENTS	30
16.1. DEFINITION OF ADVERSE EVENTS (AE)	30
16.2. DEFINITION OF SERIOUS ADVERSE EVENTS (SAE)	30
16.3. CLASSIFICATION OF AN ADVERSE EVENT	30
16.4. TIME PERIOD AND FREQUENCY FOR EVENT ASSESSMENT AND FOLLOW-UP	32
16.5. ADVERSE EVENT REPORTING.....	33
16.6. SERIOUS ADVERSE EVENT REPORTING.....	33
16.7. REPORTING EVENTS TO PARTICIPANTS	34

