6. STUDY POPULATION

On Day 1, participants must be qualified to participate and baseline assessments are performed prior to the first administration of the study drug.

[REDACTED]

Inclusion criteria:

1. Male or female, aged ≥ 18 years of age
2. Participants must have all of the following **in at least one eye**:
 - More than 10 lashes with collarettes / cylindrical dandruff present on the upper lid
 - Presence of one or more mites with lash epilation of the upper and lower lids
 - For the 15 glands evaluated on the lower lid, have evidence of meibomian gland dysfunction based on a total meibomian gland secretion score between 12 to 32
 - Have at least Grade 1 erythema of the lower lid
 - Fluorescein tear breakup time < 10 seconds
 - Per meibography, the participant must have intact partial to full meibomian glands in at least 33% of the total meibomian gland area of the lower lid in the opinion of the investigator

[REDACTED]

[REDACTED]

[REDACTED]

4. Have a corrected distance visual acuity better than or equal to logMAR $+0.7$ as assessed by the Early Treatment of Diabetic Retinopathy Study (ETDRS) scale in each eye at Day 1
5. Willing to sign the informed consent, deemed capable of complying with the requirements of the study protocol and stated willingness and availability to comply with all study procedures for the duration of the study
6. For females of childbearing potential: use of acceptable methods of contraception* for at least 1 month prior to Day 1 and agreement to use such a method during study participation and for an additional four weeks after the end of study drug administration

Exclusion criteria:

1. Have used any artificial tear product within 24 hours of Day 1 or anticipated use during the study (with the exception of rescue therapy described in Section 15 of the protocol)
2. Use of systemic antihistamines within 30 days of Day 1

7. Treatment of blepharitis within 14 days of Day 1 (e.g., topical tea tree oil or hypochlorous acid) or unwilling to forego the use of these treatments for the duration of the study
8. The use of lid hygiene products such as lid scrubs, warm compresses or lid massage within 7 days of Day 1 or unwilling to forego the use of these treatments for the duration of the study

[REDACTED]

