8. CLINICAL EVALUATIONS

8.1. DAY 1

At the Day 1 visit, potential participants will be evaluated for eligibility and, if qualified, enrolled in the study. Prior to performing any study-specific procedures, potential participants must provide informed consent using the current IRB-approved informed consent form.

If potential participants fail to meet eligibility criteria, they can be screened one additional time on a different day. Rescreened participants should be assigned the same participant number that was used for the initial screening.

Procedures to be performed at the Day 1 visit include:

- Obtaining informed consent
- Obtaining the medical and ophthalmic history; concomitant medications
- CDVA

[REDACTED]

[REDACTED]

- TBUT
- Slit lamp biomicroscopy, including assessment of lid margin erythema
- Meibomian gland secretion assessment of lower lids

There will be two dosing arms, a BID active dosing and a TID active dosing arm.

Participants will be instructed to administer a single drop per eye from the first bottle in the morning and evening; a single drop per eye from the second bottle should be administered in the afternoon. The treatment period will be for approximately 85 days.

At Day 1, site staff will supervise the participant's first dose of the study medication. Participants should wash their hands prior to administration of the dose. Following drop administration, the participant will be asked to close their eyes for approximately 15 to 30 seconds and apply gentle pressure to the upper lid to express the medication across the upper and lower lid margins. The participant should be instructed to let the medication air dry on the lid without dabbing with a tissue.

On the day of in-office study visits, participants will be instructed not to use the study medication prior to the visit; the study medication can be administered after the visit has been completed.

If a dose is missed, participants will be instructed to administer the drop if it is at least an hour prior to the next dose. If it is less than an hour, the participant should simply dose the next drop.

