12. STATISTICAL CONSIDERATIONS AND ANALYSIS

12.1. SAMPLE SIZE

There is no prior data available for TP-03 in the treatment of MGD to use as a performance estimate. The sample size of 40 participants was selected based on clinical and practical considerations. Results from this study will be used to inform the design of subsequent studies to demonstrate a therapeutic effect.

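### The BID–TID comparison of MGSS uses an unadjusted change score; adjusting for Day 1 MGSS could recover roughly 0 to 13 of 40 participants' worth of information, depending on assumptions, at a worst-case cost of about 1

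*Protocol*

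**What the plan says.** Protocol 12.7 says "Efficacy analyses comparing the outcome between dosing regimens will be performed on the change from baseline", with the post-treatment survey excepted, "using either the Student's *t*-test or Wilcoxon rank-sum test as appropriate". The Protocol Summary says the same: "Efficacy measures will be compared between dosing regimens as the change from baseline using either the t-test or Wilcoxon rank-sum test as appropriate". SAP Section 1 repeats that sentence. No readable text adjusts the BID–TID comparison for the Day 1 value.

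MGSS is "computed as the sum of the grades for all 15 glands evaluated on the lower eyelid with a range from 0 to 45" (Protocol 12.5). It is measured at Day 1 (Protocol 8.1: "Meibomian gland secretion assessment of lower lids") and again at every later visit. Eligibility requires evidence of MGD "based on a total meibomian gland secretion score between 12 to 32" in at least one eye (Protocol 6). The clinical hypothesis is that "TID will result in a greater improvement from baseline than BID treatment for 85 days". Protocol 12.1 reports no prior data for TP-03 in this condition and adds: "Results from this study will be used to inform the design of subsequent studies to demonstrate a therapeutic effect".

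Most of SAP 2.2.8, Efficacy Analyses, cannot be read in this copy. An adjusted model may be there.

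**The concern.** A t-test on change scores is a regression of the follow-up value on regimen with the Day 1 coefficient set to 1. ANCOVA fits the same model but estimates the coefficient. Both give an unbiased TID–BID difference under randomisation, and ANCOVA is generally the more precise. The gain is largest when the true slope is far from 1 and disappears when it is near 1. With no prior data, the plan has no stated basis for taking the slope to be 1.

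BID versus TID is the only randomised contrast in the trial, and its estimate is meant to feed the design of later studies. With at most 40 participants the interval will be wide, so unused precision matters, particularly when the covariate is already collected.

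**Working it through.** The plan has no figure to reproduce here: 40 was not derived from an effect size, SD or power.

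**Inputs from the documents.** N = 40 at most, allocated 1:1, so 20 per arm. Two-sided α = 0.05 (Protocol 12.3). MGSS range 0 to 45; Day 1 entry window 12 to 32.

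**Assumptions.** All 40 are analysed with one MGSS value each. ρ is the correlation between Day 1 and follow-up MGSS, taken as 0.3, 0.5 or 0.7. k is the Day 1 SD divided by the follow-up SD, taken as 1.0, 0.8 or 0.7. The power illustration uses a difference of 0.8 follow-up SD.

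**Formulas** (follow-up SD = 1):

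- True slope = ρ/k.
- Variance per participant, change score: V_c = 1 + k² − 2kρ.
- Variance per participant, ANCOVA: V_a = (1 − ρ²) × 37/36, where 37/36 = 1 + 1/(N − 4) is the cost of estimating one slope at N = 40.
- Ratio R = V_a/V_c. Information lost by the change score = 40(1 − R). ANCOVA on 40 is worth 40/R by change score.
- 95% half-width = t × √(2V/20), with 38 df (t = 2.024) for change and 37 df (t = 2.026) for ANCOVA. Power is from the noncentral t.

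**Worked case, k = 1.0, ρ = 0.5.** V_c = 1 + 1 − 1 = 1.00. V_a = 0.75 × 37/36 = 0.771. R = 0.771. Lost: 40 × 0.229 = 9.2. Equivalent N: 40/0.771 = 52. Half-widths: 2.024 × √0.1 = 0.64 and 2.026 × √0.0771 = 0.56.

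| k | ρ | R | Lost of 40 | Half-width, change → ANCOVA | Power, change → ANCOVA |
|---|---|---|---|---|---|
| 1.0 | 0.3 | 0.67 | 13.3 | 0.76 → 0.62 | 55% → 72% |
| 1.0 | 0.5 | 0.77 | 9.2 | 0.64 → 0.56 | 69% → 80% |
| 1.0 | 0.7 | 0.87 | 5.1 | 0.50 → 0.46 | 89% → 92.5% |
| 0.8 | 0.3 | 0.81 | 7.7 | 0.69 → 0.62 | 63% → 72% |
| 0.8 | 0.5 | 0.92 | 3.3 | 0.59 → 0.56 | 77% → 80% |
| 0.8 | 0.7 | 1.01 | −0.3 | 0.46 → 0.46 | 92.8% → 92.5% |
| 0.7 | 0.3 | 0.87 | 5.0 | 0.66 → 0.62 | 66% → 72% |
| 0.7 | 0.5 | 0.98 | 1.0 | 0.57 → 0.56 | 79% → 80% |
| 0.7 | 0.7 | 1.03 | −1.1 | 0.46 → 0.46 | 93.2% → 92.5% |

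Negative entries favour the change score. Its best case is a true slope of exactly 1 (ρ = k). Then V_c = 1 − ρ², so R = 37/36 = 1.028 and ANCOVA loses about 1 participant.

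**Which k is plausible.** The entry window restricts Day 1 MGSS but not follow-up MGSS. As an illustration, a normal score with mean 22 and SD 6, cut to 12–32, keeps an SD of 4.8, and 4.8/6 = 0.80. So k below 1 is credible, and that shrinks the gain.

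**Simulation** (20,000 trials per setting, same grid). Null rejection was 0.048 to 0.053 for both methods. Mean estimates were 0.796 to 0.803 for a true 0.8 under both. Simulated variance ratios agreed with the formula to within about 0.02.

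**The case against.** The strongest reply is that this is a preference. The trial is an exploratory pilot with no power target, the planned test is valid, and change from baseline speaks directly to the hypothesis. All of that is true, and it is why the point concerns precision only. But ANCOVA does not change the question. With Day 1 MGSS in the model, the regimen difference is identical whether the outcome is Day 85 MGSS or change to Day 85.

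The second reply is that the gain may be small, and this stands. In the six cells with k below 1 the losses are about 8, 3, 0, 5, 1 and −1, with a median of 2. Extending the same formula at ρ = 0.3, 0.5, 0.7 gives about 3, −1 and 0 for k = 0.6, and 1, −1 and 2 for k = 0.5. Nor is 13 a ceiling: equal SDs with ρ = 0.2 give about 15. The range describes the assumptions, not a bound for this trial. The case for ANCOVA is the asymmetry: an unknown gain against a cost of at most about 1 participant.

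Third, the figures cover the t-test only, and the plan also allows Wilcoxon. They assume full follow-up and one value per participant, while the unit of analysis is not visible. These limits stand. With 36 evaluable the worst-case cost is still about 1 participant.

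Finally, SAP 2.2.8 may already contain an adjusted model, and SAP Section 1 only restates the protocol. The claim therefore rests on Protocol 12.7 and the two summaries.

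**Conclusion.** The concern holds as a recommended improvement (should, not must), with medium confidence. The readable plan fixes at 1 a slope it has no data to support. For the MGSS t-test with 20 per arm analysed, estimating the slope recovers about 5 to 13 of 40 participants' worth of information if k = 1.0 and about 0 to 8 if k = 0.8, for correlations of 0.7 down to 0.3. At worst it costs about 3% in variance. Neither bias nor type I error is at issue. No gain has been computed for the Wilcoxon option or for graded erythema.

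**What to change.** In Protocol 12.7, both summaries and the SAP, specify for MGSS an ANCOVA with regimen and Day 1 MGSS as terms. Take Day 85 as the main comparison, since it matches the 85-day hypothesis and the database lock that precedes unmasking. Report the adjusted TID–BID difference with its 95% CI, and keep the t-test or Wilcoxon test on change as a sensitivity analysis.

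For graded lid margin erythema, name one baseline-adjusted method, such as rank ANCOVA on the Day 1 grade. This is secondary, and the MGSS change does not depend on it.

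If SAP 2.2.8 already contains an adjusted model, bring Protocol 12.7 and the two summaries into line with it instead.

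The cost is wording, one model statement and one degree of freedom. No new data are needed.

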12.2. RANDOMIZATION

This is a randomized, double-masked study. A blocked randomization schedule will be prepared and used to package the afternoon dose of the drug (all participants receive TP-03 for the morning and evening doses). The drug will be dispensed at the site sequentially from the available inventory. The bottle number dispensed will be recorded.

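### Does the pooled one-sided test of improvement from Day 1 need a stated limit, given that every participant receives TP-03?

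*Protocol*

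**What the plan says.** Protocol 12.7, under its efficacy heading, plans two things. The regimens are compared on change from baseline with a t-test or rank-sum test. The combined sample is then tested for change from baseline with a paired t-test or signed-rank test: "A one-sided test for an improvement from baseline will be evaluated using an α of 0.025".

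Protocol 12.6 gives the hypotheses for the combined test: "the null hypothesis is there is no difference between the baseline and follow-up values", and "The alternative hypothesis is the follow-up outcome has improved from baseline". Neither mentions a control or a drug effect.

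Protocol 12.2 confirms that "all participants receive TP-03 for the morning and evening doses". Vehicle serves only to mask the afternoon dose of the BID arm (Protocol 3.1 and 12.2).

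Day 1 is both the qualifying and the baseline visit: "On Day 1, participants must be qualified to participate and baseline assessments are performed prior to the first administration of the study drug". Both efficacy outcomes visible in Protocol 12.5 are also entry criteria in Protocol section 6: "Have at least Grade 1 erythema of the lower lid" for erythema and, for the secretion score (MGSS), "have evidence of meibomian gland dysfunction based on a total meibomian gland secretion score between 12 to 32".

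Four places bear on how the combined test may be read. Protocol 12.1 reserves the demonstration of a therapeutic effect for subsequent studies. Protocol 12.8 describes the study as initial and exploratory. The protocol title calls it a pilot. SAP section 1 places the combined analysis among additional analyses.

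**The concern.** A significance test filed under efficacy invites the reading that TP-03 works. Without a concurrent control, rejection shows only that scores moved in the favourable direction after Day 1. Natural course, study participation and regression to the mean can all move them.

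Regression to the mean deserves particular attention for erythema. The entry cut has one end, and the same Day 1 grade serves as baseline. Eyes that qualified partly through a high reading on the day will tend to look better later, even untreated. Rescreening can add to this: "If potential participants fail to meet eligibility criteria, they can be screened one additional time on a different day".

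The results are meant to inform later studies, so a significant pooled p-value could be carried into planning as a TP-03 effect. No visible text states that the analysis is uncontrolled. SAP 2.1 also words the objective as the efficacy of TP-03, without the regimen comparison that appears in Protocol section 4 and SAP section 1.

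**Working it through.** **The plan's own figures.** The sample size of 40 has no effect size, SD or power behind it (Protocol 12.1), so there is no calculation to reproduce. The alpha levels agree with each other: one-sided 0.025 and two-sided 0.05 share the critical value z = 1.960. The level of the test is not in question.

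**How much non-drug change is enough.** With n = 40 the critical value is t(0.975; 39 df) = 2.023. The test rejects once the observed mean improvement exceeds 2.023/√40 = 0.32 SD of the change. If the drug does nothing and the true non-drug improvement is d SDs, the rejection rate is 1 − F(2.023), where F is the noncentral t distribution with 39 df and noncentrality d√40. The values of d are assumptions.

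| d | d√40 | Rejection |
|---|---|---|
| 0 | 0 | 2.5% |
| 0.1 | 0.63 | 9.0% |
| 0.2 | 1.26 | 23.4% |
| 0.3 | 1.90 | 45.6% |
| 0.5 | 3.16 | 86.9% |

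**Erythema selection alone.** This is a simulation with no treatment effect: a stable true level plus independent visit noise, cut into grades 0 to 3, with entry at Grade 1 or more on Day 1 and trials of 40. The 0 to 3 scale, an intraclass correlation of 0.5 to 0.8, three splits of grades 1 to 3 (45/35/20, 60/30/10 and 33/34/33) and the share of otherwise eligible eyes at grade 0 are all assumptions. The rescreening column uses the 45/35/20 split only.

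| Grade-0 share | Rejection | If every eye failing the cut were rescreened once |
|---|---|---|
| 2% | 3–4% | 4% |
| 5% | 4–6% | 6% |
| 10% | 7–10% | 9–11% |
| 20% | 13–23% | 19–27% |
| 35% | 25–54% | 38–59% |
| 50% | 41–81% | 58–86% |

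The spurious mean improvement runs from 0.01–0.02 grade at a 2% share to 0.22–0.58 grade at 50%. The direction is certain; the size is not. Entry also requires collarettes, mites, an abnormal secretion score and a short tear breakup time in the same eye, so nothing in the documents points to a large grade-0 share. Those criteria need be met in only one eye, and the analysis eye is not visible. If fellow eyes enter the analysis, the bias is diluted.

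**MGSS.** The window has two ends. With an assumed SD of 8 and the source mean at the window centre, (12 + 32)/2 = 22, rejection is 2.1–2.8%, essentially nominal. With the mean 4 points off centre it is 8–15% on one side and 0.2–0.6% on the other. The visible text does not give the direction of the scale, so no sign can be assigned.

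**Randomised comparison.** Selection acts alike in both arms and cancels on average. The two-sided BID versus TID t-test on simulated erythema, 20 per arm, rejects in 4.6–5.2% of trials (nominal 5%).

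**What the test shows against what the plan claims.** The test can establish change from Day 1. Protocol 12.6 claims change from Day 1. No visible passage in either document claims that the pooled test demonstrates a TP-03 effect, and Protocol 12.1 assigns that task elsewhere. The two match.

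**The case for a change.** The best case for a change is that the limiting statements apply to the study as a whole and not to this test, that the efficacy heading and the loose objective in SAP 2.1 pull the other way, and that a caveat would cost a few sentences before the Day 85 lock. It can also be argued that elements common to both arms could produce improvement by themselves: lid pressure at dosing, no contact lenses, and saline as needed.

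The logic about control stands, and so does the direction of the erythema bias. The rest is weaker.

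- **Shared elements do not all point one way.** The pressure at dosing is gentle and on the upper lid, whereas secretion is scored on the lower lid, and lid massage is barred (Protocol section 6, exclusion 8). Contact lenses stop at least 7 days before Day 1 (exclusion 11). Saline is not to be used before a visit on visit days (Protocol section 15). Giving up artificial tears, blepharitis treatment and lid hygiene (exclusions 1, 7 and 8) could worsen outcomes. The net direction is unknown.
- **A two-sided 95% interval in place of the test alters no result.** It has the same critical value. Rewording SAP 2.1 alters none either; that section is looser than the other statements of the objective but does not contradict them.
- **A pooled Day 15 to Day 85 analysis is a trade-off, not a repair.** It removes most of the entry-selection bias (simulated rejection 2.2–2.8%). It remains uncontrolled, and it discards any response before Day 15, so a fast-acting drug could look inert.
- **The missing sentence may not be missing.** The SAP contents list places Efficacy Analyses at page 10 and Safety Analyses at page 15. Nearly all of that efficacy text is unavailable, and it is where such a caveat would sit.

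**Conclusion.** No change to the plan. The pooled test is an uncontrolled before-and-after analysis and cannot isolate a TP-03 effect, but the plan does not ask it to: the stated hypothesis is improvement from baseline, in an exploratory pilot that leaves therapeutic effect to later studies. What remains is a point of interpretation that a competent report would make anyway, namely that the pooled change has no concurrent control and describes change from Day 1 only. Saying so in the final report is sensible but optional.

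The size of any misreading cannot be fixed from the documents. For erythema, selection alone could leave rejection near nominal (3–4%) or raise it to 81%, or 86% with universal rescreening, depending on an assumed grade-0 share, grading scale and visit-to-visit correlation. For MGSS the bias may be nil or run either way. The conclusion depends on none of these inputs: it rests on the wording of Protocol 12.1, 12.6 and 12.8 and SAP section 1, and on the randomised BID versus TID comparison being unaffected. It would need another look only if the unavailable SAP text presented the pooled test as proof of a TP-03 effect.
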